# 10.5.4 Exposure to Investigational Product

Descriptive statistics will be produced to describe the exposure to investigational product including patient-month exposure to IP, number of doses, duration of dosing, number of missed doses, and maximum number of days between doses.

### 10.5.5 Exposure to Concomitant Medication

A summary of all concomitant medications reported in at least 5% of the subjects will be provided by preferred term as coded by the World Health Organization Drug (WHODRUG) dictionary.

### 10.5.6 Other Safety

The analyses of subject incidence of all treatment-emergent, serious, treatment-related, serious treatment-related, those leading to withdrawal of investigational product, those leading to study withdrawal, fatal, and fatal treatment-related adverse events tabulating by system organ class and preferred term in descending order of frequency will be repeated by the reasons of apremilast failure at screening: 1) failure to achieve adequate response, 2) loss of adequate response or 3) intolerability.

# 11. Changes From Protocol-specified Analyses

The analyses on all the efficacy and safety endpoints will be repeated by the reasons of apremilast failure at screening: 1) failure to achieve adequate response, 2) loss of adequate response or 3) intolerability. This was not pre-specified in the protocol but will be conducted to assess the potential bias of how the different reasons of apremilast failure would impact the efficacy and safety endpoints in this study.

### Appendix A. Technical Detail and Supplemental Information Regarding Statistical Procedures and Programs

### Visit Windows for All Efficacy and Selected Safety Evaluations

Per protocol, visits are to be performed within 5 days of the protocol-specified study day. To allow for variations in scheduling, the following visit windows will be applied to all efficacy and select safety evaluations (ie, vital signs, laboratory evaluations, and physical measurements) to assign a most appropriate nominal visit for analysis. If more than one actual visit falls within the same defined window, the closest visit to the target day (ie, scheduled visit week x 7 + 1) will be considered for analysis. If two assessment dates are the same distance from the target day, then the latest visit will be considered for analysis. Any visit that falls in an unscheduled visit for that assessment (eg, a DLQI assessment done at week 16) will be excluded from the analysis and reported in listings only.

Visit	Target	Window	Interval
Week	Day	Definition	(days)
Baseline	1	Last Evaluation prior to or on Study Day 1	n/a
Week 4	29	Study Day 15 to 42	28
Week 8	57	Study Day 43 to 70	28
Week 12	85	Study Day 71 to 98	28
Week 16	113	Study Day 99 to 126	28
Week 20	141	Study Day 127 to 154	28
Week 24	169	Study Day 155 to 182	28

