6.1.1.1 Dosage, Administration, and Schedule

Etanercept dosing will follow the recommended label dosing for patients with PsO: 50 mg subcutaneously, twice weekly for 12 weeks followed by 50 mg subcutaneously once weekly (for the additional 12 weeks).

Each dose of etanercept will consist of the complete contents of 1 pre-filled syringe. Injections should occur in the thigh, abdomen or outer area of the upper arm. The injection site should be rotated with each dose.

During the first 12 weeks of the study, subjects will receive 2 doses of etanercept per week (eg, on Monday and Thursday). During the second 12 weeks of the study, subjects will receive 1 dose of etanercept per week (scheduled approximately 7 days apart). Throughout the entire trial, administration of etanercept should occur on the scheduled day; however, if unavoidable, it may be given earlier or later as long as the dose is not within 2 days of the next scheduled dose. If the dosing window is missed,

that dose should be skipped. Subsequent doses of etanercept should resume on the original schedule. If etanercept is to be taken the day of a study visit, it must be taken after the study visit has occurred.

Injections of etanercept will be administered by the subject or a caregiver. The individual administering the dose must demonstrate to the site staff that he or she is competent to correctly administer the subcutaneous doses. The first dose of etanercept must be administered at the study site. All subsequent doses will be administered at the subject's location on the scheduled dose day. Supplies of etanercept will be dispensed to subjects for administration at home. The subject will be instructed in appropriate handling and storage of used and unused syringes.

The dose, start date, stop date, dose time and box number of etanercept are to be recorded on each subject's CRF.

The effects of overdose of etanercept are not known.

There may not be any adjustment of etanercept dosage other than the protocol-specified reduction from 50 mg twice weekly for the first 12 weeks of the study to 50 mg once weekly for the second 12 weeks.

Please refer to the US Prescribing Information or the Etanercept Investigator's Brochure for the most recent safety information.

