7.2.3 Treatment

Visits will occur per the Schedule of Assessments (Table 1) during the treatment period from day 1 (baseline) through week 24. On-study visits may be completed within ± 5 days of the target visit date. Prior to enrollment, subject eligibility must be confirmed with screening procedures. Subjects satisfying eligibility requirements will be enrolled. The date of the first dose of etanercept is defined as day 1 (baseline). All subsequent doses and study visits will be scheduled based on the day 1 date.

Etanercept is to be administered at the site after all assessments have been done for all visits that will include dosing. Subjects ending the study prior to week 24 will be asked to complete the unscheduled early termination (ET) visit assessments which are the same as those listed in the Schedule of Assessments under Week 24/ET.

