# 4.1.2 Secondary Efficacy Endpoints

- PASI 75 at all other visits
- PASI 50 and 90 at all visits
- Percent PASI improvement from baseline at all visits
- sPGA of 0 or 1 at all visits
- sPGA of 0, 1, or 2 at all visits
- sPGA at all visits
- One and two grade improvement from baseline in sPGA at all visits
- Percent BSA improvement from baseline at all visits
- PSI total and component scores at all visits
- Patient Assessment of Treatment Satisfaction at week 12 and 24
- DLQI improvement from baseline at week 12 and 24

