# 9.3.2 Missing Post-baseline Evaluation

Subjects with missing post-baseline efficacy data will be imputed using the last observation carried forward (LOCF) method for the primary analysis for all efficacy endpoints. For LOCF imputation, missing post-baseline efficacy data will be carried forward from the last non-missing post-baseline value for that endpoint. Baseline efficacy data will not be carried forward to any missing post-baseline value.

For the primary endpoint, PASI 75 at week 12, missing post-baseline efficacy data will also be imputed using non-responder imputation as a sensitivity analysis. For non-responder imputation, the missing binary endpoint will be imputed with a value of zero to indicate no response. Patients without at least one post-baseline observation will also be defined as non-responders for the NRI analysis.

Missing post-baseline safety data will not be imputed.

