# 10.4 Efficacy Analyses

The primary analysis for all efficacy endpoints will be conducted using the full analysis set.

For the primary analysis, all efficacy endpoints will be analyzed using LOCF method for missing data imputation. For all the efficacy endpoints, analyses on observed cases will be performed as sensitivity analyses. In addition, a sensitivity analysis for the primary endpoint will be performed using non-responder imputation as described in Section 9.3.2.

Summary statistics will be generated as well as 95% confidence intervals for the estimated responses. For absolute improvement and percent improvement endpoints, both 95% confidence intervals and p-values will be provided. No multiplicity adjustments will be made for the p-values.

	dpoint Summary Table	
Endpoint	Primary Summary and Analysis Method	Sensitivity Analysis
Primary Endpoint		
PASI 75 at week 12	
 
Full analysis set with LOCF imputation for missing data
 
	
 
Full analysis set using observed cases
 
Full analysis set with NRI imputation for missing data
 
Full analysis set with possible covariates
 

Secondary Endpoint		

 
PASI 75 at all other visits
 
PASI 50 and 90 at all visits
 
Percent PASI improvement from baseline at all visits
 
sPGA of 0 or 1 at all visits
 
sPGA of 0, 1, or 2 at all visits
 
sPGA at all visits
 
One and two grade improvement from baseline in sPGA at all visits
 
Percent BSA improvement at all visits
 
PSI total and component scores at all visits
 
Patient Assessment of Treatment Satisfaction at week 12 and 24
 
Exploratory Endpoints
 
	
 
Full analysis set with LOCF imputation for missing data
 
	
 
Full analysis set using observed cases
 

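### The SAP's visit windows have no early-termination exception, so as written early-termination DLQI and satisfaction values on Days 15-70 and 99-154 are listed but not analysed; separately, the protocol's worst-toxicity laboratory shift table is absent from the SAP

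*SAP*

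**What the plan says.** **Visit windows.** SAP Appendix A gives six 28-day windows, for weeks 4 to 24, which are "applied to all efficacy and select safety evaluations (ie, vital signs, laboratory evaluations, and physical measurements". Values are placed by study day. There is no row or exception for ET. The exclusion rule reads: "Any visit that falls in an unscheduled visit for that assessment (eg, a DLQI assessment done at week 16) will be excluded"; such values go to listings.

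**Collection.** Protocol Table 1 schedules DLQI, treatment satisfaction, hematology and chemistry after baseline at week 12 and in the column headed Week 24/ET. Protocol 7.2.3 says: "Subjects ending the study prior to week 24 will be asked to complete the unscheduled early termination (ET) visit assessments". These are the week-24 assessments. The DLQI endpoint is "DLQI improvement from baseline at week 12 and 24", and satisfaction is reported at the same two weeks.

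**Missing data.** SAP 9.3.2 says that "missing post-baseline efficacy data will be carried forward from the last non-missing post-baseline value for that endpoint", and also: "Baseline efficacy data will not be carried forward to any missing post-baseline value". SAP 10.4 adds: "For all the efficacy endpoints, analyses on observed cases will be performed as sensitivity analyses". Non-responder imputation is planned only for PASI 75 at week 12. Safety data are not imputed.

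**Laboratory toxicity.** Protocol 10.3.3 promises shift tables of each subject's worst on-study toxicity grade against baseline. SAP 10.5.2 gives by-visit summaries, by-visit toxicity summaries and the subject incidence of grades 3 and 4, but no shift table. SAP 11 declares one change only, the repetition of analyses by reason for apremilast failure.

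**The concern.** Two SAP rules meet on the same values and give different answers. Appendix A excludes an off-schedule DLQI or satisfaction value from analysis; 9.3.2 would carry that value forward as the latest post-baseline one. In the SAP text available, nothing says which rule governs. ET is the main protocol-mandated way for such a value to arise, because Table 1 plans no DLQI at weeks 4, 8, 16 or 20.

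At stake is who is counted in the week-12 and week-24 patient-reported tables, and which treatment phase a carried week-24 value describes. Also at stake is whether the observed-case analysis checks anything at week 12. For laboratory data, a by-visit summary cannot show each subject's worst grade relative to baseline, which is what the protocol promised.

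**Working it through.** **1. The SAP's own window table.** Target day = 7 × week + 1, which gives 29, 57, 85, 113, 141 and 169 for weeks 4 to 24. Window length = last day − first day + 1; for week 4, 42 − 15 + 1 = 28, and the other five windows are also 28. All the stated figures reproduce.

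**2. What happens to a value scheduled only at weeks 12 and 24 (DLQI, satisfaction).**

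| Study day of ET | Appendix A, as written | LOCF in 9.3.2, read literally |
|---|---|---|
| 2-14 | no window; handling unstated | ET value carried to weeks 12 and 24 |
| 15-70 (weeks 4 and 8; 56 days) | listings only | ET value carried to weeks 12 and 24 |
| 71-98 | analysed as week 12 | the same, then carried to week 24 |
| 99-154 (weeks 16 and 20; 56 days) | listings only | ET value carried to week 24 |
| 155-182 | analysed as week 24 | the same |
| after 182 | no window; handling unstated | post-baseline, not limited by 9.3.2 |

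Excluded days: 56 + 56 = 112.

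**3. Consequences if windows are applied before LOCF.**

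- ET on Days 15-70: the ET value is normally the only post-baseline one. It is excluded and baseline is not carried forward, so the subject has no value at week 12 or week 24.
- Week 12 overall: no value from the week-4 or week-8 window is eligible, so LOCF has nothing to carry. The LOCF table equals the observed-case table, unless a Day 2-14 value were admitted under some unstated rule.
- ET on Days 99-154, with a week-12 value on file: week 24 takes the week-12 value. With week 12 on Day 85, it is older than the unused ET value by 99 − 85 = 14 to 154 − 85 = 69 days. With the ±5-day visit allowance (Days 80-90), the range is 99 − 90 = 9 to 154 − 80 = 74 days. The carried value comes from about the end of the twice-weekly phase. The unused one comes from the later phase, for which the protocol says: "During the second 12 weeks of the study, subjects will receive 1 dose of etanercept per week".

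**4. Size at week 12.** The documents give no dropout rate or timing, so the number affected cannot be computed. A ceiling can. Take 80 subjects, k of them with an excluded ET DLQI on Days 15-70 and the rest observed. Let p be the responder proportion among the 80 − k, and q the number of responders among the k (0 to k). The shift is

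p − [(80 − k)p + q]/80 = (kp − q)/80.

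Its largest absolute value is k/80, reached at p = 1, q = 0 or at p = 0, q = k.

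| Assumed k | Week-12 denominator | Ceiling (percentage points) |
|---|---|---|
| 1 | 79 | 1.25 |
| 4 | 76 | 5 |
| 8 | 72 | 10 |

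These are maxima, not expected shifts. To place k, assume that 5% to 20% of 80 subjects (4 to 16) terminate early, evenly over Days 2-168 (167 days), and that all attend the ET visit. The number on Days 15-70 is then 4 × 56/167 = 1.3 to 16 × 56/167 = 5.4, and the same on Days 99-154.

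**5. PASI 75.** PASI is scheduled at every visit from week 4 to week 24, so no window in Days 15-182 is unscheduled for it. The exclusion rule does not touch the primary endpoint.

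**6. Laboratory tables.** Set side by side, protocol 10.3.3 has worst on-study grade against baseline, SAP 10.5.2 has toxicity by visit plus grade 3 and 4 incidence, and SAP 11 does not mention the difference. Safety data are not imputed, so the LOCF conflict does not arise here. The shift-table gap stands on its own.

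**The case against.** The best defence is that Appendix A is the specific rule and 9.3.2 the general one: analysis values are defined first and carried forward second. That is an ordinary reading and it removes the formal contradiction. It does not change the result in step 3: values that the protocol asks for at ET are still left out.

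A second defence is that Table 1 pairs week 24 with ET, and the SAP's End of Study Date treats the two visits as counterparts, so an exception could be inferred. Appendix A does not state one, protocol 7.2.3 calls the ET visit unscheduled, and the pairing would not say to which analysis visit a Day-40 value belongs.

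A third stands in part. SAP 10.4.3 refers to Appendix C for the analysis of the patient-reported outcomes, and only that appendix's heading is available here. It may hold only the forms, but a rule for ET values there cannot be ruled out.

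Three stronger readings are tempting and not supported:

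- A reader might infer that grade 3 or 4 results at ET, or an abnormal result followed by a retest nearer the target day, would drop out of the incidence table. SAP section 6 defines subject incidence by at least one reported occurrence, counted once per subject, and 10.5.2 does not tie this incidence to visits. That favours use of all results.
- A reader might infer that ET values on Days 2-14 are excluded too. They have no window, so their handling is unstated.
- A reader might infer that the shift table was withdrawn. The SAP is silent on it.

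**Conclusion.** The point holds as a minor one, with moderate confidence. As written, Appendix A sends ET values of DLQI and satisfaction on 112 study days to listings, while 9.3.2 sets no such limit on LOCF. If windows come first, subjects with ET on Days 15-70 are absent from both time points, and the week-12 sensitivity analysis repeats the main table. After ET on Days 99-154, week 24 rests on a value 9 to 74 days older than one already collected, given a week-12 visit on Days 80-90.

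The effect is confined to descriptive secondary endpoints. Its size depends on an unknown number of early terminations and is bounded at week 12 by 1.25 points per affected subject, assuming 80 subjects and all others observed.

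The missing shift table is a separate, undeclared difference between protocol and SAP and needs no assumption.

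**What to change.** - **Appendix A.** State that the windows define the observed-case visits, and that ET values of DLQI and satisfaction are valid post-baseline values for LOCF at the next scheduled time point (week 12 or 24) and any later one. State how values on Days 2-14 and after Day 182 are handled.
- **SAP 10.5.2.** Restore the worst on-study toxicity shift table, derived from all post-baseline results including ET and unscheduled ones. Keep windows for by-visit summaries only. Add one sentence confirming that grade 3 and 4 incidence also uses all post-baseline results.

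The cost is a few sentences and minor programming, with no new data. The downside is that an early ET value may stand in for week 12 or 24, as LOCF already implies for PASI. The change should be made before data lock, so that the choice between readings does not follow the results.

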# Appendix B. Code Fragments

Appendix C. Patient-reported Outcome Forms/Instruments

### Appendix D. Reference Values/Toxicity Grades

Adverse event severity is graded based on the National Cancer Institute Common Toxicity Criteria for Adverse Events (CTCAE) version 4.0 (see Protocol Appendix B).

Laboratory toxicity is graded based on the National Cancer Institute Common Toxicity Criteria (CTC) version 4.0 with the following additions:

	Grade				
	0	1	2	3	4
BUN	WNL	>1.5 – 2.0 x ULN	>2.0 – 3.0 x ULN	>3.0 – 4.0 x ULN	>4.0 x ULN
HGB	WNL	>ULN	>(ULN+1) – (ULN+2)	>(ULN+2)	-
Urine Protein	NEG, NEGATIVE, TRACE, NORMAL, NOT DETECTED	+, +1, 1+	++, +2, 2+, +++, +3, 3+	++++, +4, 4+	-
Platelet Count	WNL	> ULN - 1.0x10  /L	> 1.0x10  /L	-	-
Leukocyte Count	WNL	> ULN 2.0x10  /L	> 2.0x10  /L - 4.0x10  /L	> 4.0x10  /L	-
